***Subject Recruitment:***

- [name], who is a radiologist involved in clinical imaging protocols of patients, will recruit patients who are suitable for study participation as they present to the UWHC, UWMF, WIMR, or HERI for clinical imaging or patients who contact him in response to the recruitment flyer. [name] or an authorized member of his staff will invite them to participate in the study.

- Candidates identified for past research in [name] group will be identified through participant records for these protocols ([name] 2015-0469 and [name] 2013-1561). Initial contact will be made by members of the study team of each of those projects. Subjects who expressed a written wish not to be contacted for further research (as recorded on their Informed Consent form for those protocols) will be omitted.
- The study coordinator will be involved in recruiting potential patients referred by the methods above, or patients who contact by telephone or email in response to the recruitment flyer.
- Clinicians involved in the direct care of patients may send recruitment letters to eligible patients and recruit them for the study [recruitment letter attached].
- Recruitment flyers [attached] will be posted at different locations such as the UWHC, the School of medicine, UW libraries, the University Station Clinic, St. Mary's hospital, Meriter hospital, Madison public libraries, stroke support and other aging support group locations, and on the web pages of Principal Investigator [name] (<http://uwbadgerlab.engr.wisc.edu>) and Co-Investigator [name] (<http://vplab.psychiatry.wisc.edu/>).
- Study details will be described to the potential participant by a member of the study team. If the patient expresses willingness to participate in the study, his/her name will be forwarded to the research study coordinator for further follow-up, phone screening, and recruitment according to a screening script [attached in IRB application]. Interested patients may also be asked to directly contact the research study coordinator for further information and screening.
- Participants responding to the recruitment flyer will be contacting the research coordinator. Potential patients will be screened over the phone per the screening script to determine eligibility.
- Healthy volunteers will be recruited through volunteer databases maintained by the Radiology Department (Radiology Volunteer Database, Protocol #2012-0303). Study staff involved with the maintenance of the Radiology Volunteer Database will make initial contact with prospective participants, following procedures established in that protocol. Staff will provide basic study information: the name of the study, the number of visits required, information about the fMRI scan (e.g., it does not involve a contrast agent), and the monetary compensation for participating. For subjects who agree to be contacted further, staff will provide contact information to members of the present study's team who are members of the Radiology Department. This database is available for use as described to all Radiology department faculty, and to our study team through the Radiology appointment of Co-I [name].
- Healthy volunteers may be recruited through flyers posted across the UW campus and downtown Madison.

- Healthy volunteers may be recruited through an email blast to the UW community, through the Division of Information Technology (DoIT). [Sample text of the email is attached.]
- Healthy volunteers may be recruited through word-of-mouth.

***Subject Compensation:***

- Subjects with stroke will be paid \$20 per hour for training sessions, and \$25 per hour for fMRI scanning sessions, to compensate for their time and travel expenses.
- Healthy control subjects will be paid \$10 per hour for training and \$15 per hour for fMRI scanning sessions, to compensate for time and travel expenses.

***Privacy and Confidentiality***

All study procedures are performed in private rooms or research laboratories with closed doors, by staff that have received HIPAA training and in accordance with clinic practice. Subjects may choose not to answer any questions that make them uncomfortable or that they feel violate their privacy. All subject data, including MRI data, will be identified by a subject number. We will take every precaution to protect subject information from a breach of confidentiality with the use of electronic security measures (e.g., passwords). Additionally, paper files will be stored in a locked cabinet when not in use. Subject information will not be disclosed to anyone who is not key personnel on this study without the written permission of the subject. To the extent permitted by law, subject identity and participation in this study will remain confidential.

The subject's name, date of birth, gender, date of MRI scan, and MRI screening form will be obtained for the MRI scan log (participant info form). In addition, information from patient medical records such as medications, medical history, physical exam findings, vitals, radiological data, laboratory data, and procedures will also be collected. These questions are shown in the Health Questionnaire [attached].

The scan logs will be kept in locked cabinets. Only individuals involved with the study will have access to PHI, all identifying information, and all collected datasets which will all be stored in locked cabinets in the PI's office, study coordinator's office, or on password protected computer systems.

***Study Procedure***

***Subject Assessments***

### ***Behavioral Assessment:***

The following commonly used measures of lower extremity motor assessment, standard stroke scales, and measures of activities of daily living will be administered at starting and ending time points to all patients over the length of the study. Healthy normal controls will complete these measures at the beginning of the study. Pilot controls (enrolled before other groups as well as throughout the study for continuing development) will complete a subset as deemed necessary for preparing the study and the study team for the patient and control groups. The assessments are as follows:

1. Six Minute Walk Test (6MWT): The 6MWT is a simple series of laps along a 30 m straight path in a level hallway. Subjects will be instructed to walk as far as they can in six minutes back and forth along this path, according to standard instructions (Rehab Measures - 6 Minute Walk Test). They will be allowed to use mobility aids, to stop or to rest as necessary. Total distance walked will be recorded based on the number of laps (including any fractional last lap), as well as from the IMU motion reconstruction.
2. Timed Up-and-Go test (TUG): The TUG is a simple timed test of how long it takes to stand up, walk 10 feet, turn around, return to the starting point, and sit down. Subjects will be instructed to perform this sequence as quickly as they safely can, using standard instructions (Podsiadlo and Richardson, 1991). The test will be performed in a laboratory or hallway setting.
3. Self-Selected Walking Speed (SSWS): A simple test of the speed a person chooses to walk over a 5-meter distance.
4. Fastest Comfortable Walking Speed (FCWS): A similar test of the “fastest comfortable speed” a person can use to walk over the 5-meter distance
5. Center of Pressure (COP): Center of pressure represents the average location of the vertical force under the feet; its motion is used as an indicator of balance control. Our protocol is a modified version of the ‘Clinical Test of Sensory Interaction and Balance’ (Rehab Measures - Clinical Test of Sensory Interaction and...). COP will be recorded during two 60-second trials of standing as motionlessly as possible on a pressure platform: one with eyes open, the other with eyes closed. During the eyes-open trial, subjects will be instructed to focus their eyes on a spot on the wall a distance in front of them. Metrics of COP control will be computed, including excursion, average velocity, standard deviation, and an estimate of center of mass location (Hof, 2005).
6. Stroke Impact Scale (SIS): The Stroke Impact Scale, or SIS, was created to assess changes in impairments, activities and participation following a stroke will be used in the pre-training and post-training phase of this study. Although the SIS form allows for proxy completion, for this study, subjects will be completing the SIS themselves.
7. Mini-Mental Status Examination (MMSE): The MMSE is a screening tool that

provides a brief, objective measure of cognitive function. We will use the original standard MMSE (Folstein, 1975).

8. Center for Epidemiologic Studies-Depression Scale - Revised (CESD-R): The CESD-R is a self-report scale and includes 20 items that survey mood, somatic complaints, interactions with others, and motor functioning.
9. Electromyography (EMG) – is the recording of changes in skin voltage caused by contraction of the underlying muscles. This recording will be obtained using the EMG recording equipment incorporated in the rehabilitation cycle. EMG electrodes will be attached to the surface of the skin over selected muscles of interest in the legs. Muscles may include tibialis anterior, gastrocnemius (medial and lateral), soleus, peroneus longus, peroneus brevis, vastus medialis, vastus lateralis, rectus femoris, iliopsoas, biceps femoris (medial and lateral), semitendinosus, gluteus maximus, gluteus medius, and tensor faciae latae. Proper electrode placement is made according to recommendations from the literature (De Luca, 1997; Rainoldi et al., 2004; SENIAM). A reference electrode will be attached over a bony landmark such as the kneecap, elbow or anterior superior iliac spine (ASIS). Wires will be restrained by tight-fitting clothing, straps or skin-safe tape to prevent motion artifacts. EMG signals will be pre-amplified at the sensor site, and simultaneously recorded by (i) a computer data acquisition system, and (ii) a microcontroller used to control the robotic cycle. Electrodes will be either single-use adhesive electrodes or reusable electrodes. EMG signals will be used as input to the robotic controller as well as for evaluation of outcomes.
10. Leg strength: will be assessed using isometric contractions against the instrumented pedals of the rehabilitation cycle.
11. Health Questionnaire: to document the general physical health and social habits of all subjects.
12. Pain Scale: Patients will be asked to rate their degree of pain on a scale of 0 (no pain) to 5 (in tears).
13. Modified Ashworth Scale: will be used to assess muscle tone in each hip and knee.
14. Fugl Meyer Assessment (FMA): range of motion testing of lower and upper limb capacity. The lower-limb section of the 37-item FMA (11 items) (Hsieh et al., 2007) will be used to categorize stroke severity at the time of block randomization into one group or another. If time allows, the complete 37-item FMA will be performed instead for completeness.
15. Pre and post intervention questionnaire – a series of questions to get a sense of the patient's expectations, and general tiredness and motivation levels at the beginning and end of the study, and at the start of intervention each day. The questionnaire administered at the beginning of the study will also ask questions regarding any allergies the patient may have and his/her experience with

pedaling exercise. The post-intervention questionnaire is to get the patient's feedback regarding their experience in the study.

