**Timeline:**

- **Timepoint 1 Visit** – will include baseline behavioral assessments, gait tests,

written questionnaires, and fMRI scan

- Training session #1 : [this could occur on the same day as the first behavioral and fMRI sessions]
- Visit 2 – training session #2
- Visit 3 – training session #3
- Visit 4 – training session #4
- Visit 5 – training session #5
- Visit 6 – training session #6
- Visit 7 – training session #7
- Visit 8 – training session #8
- Visit 9 – training session #9
- Visit 10 – training session #10
- Visit 11 – training session #11
- Visit 12 – training session #12
- **Timepoint 2 Visit** – will include endpoint behavioral assessments, gait tests, written questionnaires, and fMRI scan 2 at the end of the intervention . This visit could occur on the same day as the final intervention, or the next day or two per subject and experimenter convenience.–

Each behavioral session will take roughly 1 hour. Each intervention session will take about 1 hour. Each fMRI scan session will take 2 hours. The behavioral and fMRI sessions will take place at WIMR; the training sessions will take place at the UW-Madison Mechanical Engineering Building. We will arrange and pay for transportation between sites as needed.

Evidence suggests that targeted lower limb cycle training can improve walking distance and speed in stroke patients. Some example studies used a program of 10-15 training sessions over 2-3 weeks (Brown et al., 2005; Katz-Leurer et al., 2006), and 12 sessions over 4 weeks have been used in robotic gait training (Krishnan et al., 2013). This basis suggests that the intended duration and intensity of training (12 sessions of 30 minutes over 4 weeks) will be sufficient to demonstrate improvements in gait and motor function if they occur. However, this protocol is a target, which may be adjusted for individual patients as necessary to accommodate schedules and other needs. In such cases, the goal will be to keep the total number of training sessions constant for all patients. However, if interim results [after 6-10 patients] suggest that 12 sessions is not sufficient, then the study team will make provisions to increase the number of study sessions. Finally, if it appears that the subject will take more than 15 sessions to complete the study, then subject participation in the study will end.

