### **Aerobic Training Group (Control Group): Procedure**

Patients in the Control group will perform an identical protocol to that used by the Robotic group, except that the robotically-incentivized pedaling exercise will be replaced with an aerobic therapy program. This intervention will emulate an established form of motorized pedaling therapy similar to that used in commercial motorized exercise bikes to improve underlying cardiovascular unfitness contributions to gait impairment. This therapy implements a simple version of assist-as-needed and constant-velocity control. The patient's target pedaling speed (e.g. 20 rev/min (to be finalized through pilot tests: range 15-50 rev/min) and power level (set by heart rate to require approximately 50-70% of maximal oxygen uptake, estimated individually for each patient) are set at the beginning of each session and a motor provides assistance or resistance to compensate for the performance of the patient. The exercise will be performed in this mode for 30 minutes per training session.

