## Potential Risks and Benefits

### *Cycling*

Recumbent cycling at moderate intensity is widely considered a safe activity. Nevertheless, common risks associated with exercise may also occur in this study. These risks include muscle soreness, joint soreness, a feeling of exertion, and being out-of-breath. Robotic control of the cycle means that limbs may be driven through passive movements, and may be driven opposite to the forces generated by the user, which may increase muscle soreness. As with any device, there is a slight risk of malfunction; the cycle is equipped with emergency stops on the handles that suspend operation of the motor in this event.

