### *EMG (electromyography):*

EMG is a diagnostic tool that evaluates muscle or nerve problems. It uses surface electrodes to assess the activity of muscles and the ability of motor neurons to control the muscular system. Risks associated with this procedure are minor and may include skin irritation and general soreness in the areas being tested. This may last for a few days and can be relieved with an over-the-counter pain reliever.

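### Soreness is a named cycling risk, but pain is scheduled only before and after training: session-level soreness is not systematically solicited, and no adverse-event summary by arm is planned

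*Combined protocol and SAP*

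**What the plan says.** **Risk.** Under Potential Risks and Benefits, the Cycling paragraph states: "These risks include muscle soreness, joint soreness, a feeling of exertion, and being out-of-breath". It adds that under robotic control the limbs "may be driven opposite to the forces generated by the user, which may increase muscle soreness". The risks are not ranked and no arm is named.

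**Pain measurement.** The Behavioral Assessment section introduces a numbered list of measures that "will be administered at starting and ending time points to all patients over the length of the study". Item 12 of that list is the Pain Scale, a 0-to-5 rating worded for patients, with no timing of its own. Healthy controls complete the listed measures at the beginning of the study.

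**Each session.** Item 15 is a questionnaire about what patients expect from taking part and their "general tiredness and motivation levels at the beginning and end of the study, and at the start of intervention each day". At entry it also asks about allergies and pedaling experience. The version after the intervention asks for feedback on taking part.

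**Safety reporting.** The Data and Safety Monitoring Plan has the principal investigator review adverse events and problems when they arise and report them to the IRB, with continuous monitoring. The section on minimizing risks says subjects are always supervised and can make discomfort known. Neither section describes a solicited question or a recording form.

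**Analysis.** The Behavioral Data section plans a Group by Time model on the fMRI signal change and all the behavioral scores. Neither Data Processing/Data Analysis nor Sample Size mentions a summary of adverse events or tolerability by arm.

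**The concern.** The protocol identifies a plausible harm and has a scale for it, but uses the scale at the two points least able to show what happens during training. Soreness that appears after an early session and has gone by the end visit leaves no trace unless someone mentions or notices it. Volunteered reports depend on the patient and on the staff member present, so they are a weak basis for comparing two regimens.

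This matters because of what the pilot is for. The robotic therapy description says the study is partly intended to choose among therapy designs, that task difficulty will rise as skill grows, and that early patients' experience may change the task. The Timeline section allows more sessions to be added after 6 to 10 patients. These decisions would be made without systematic tolerability data. A patient who leaves because of soreness may also have no ending pain score, so the pre/post comparison could lose its most informative cases.

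**Working it through.** This is mainly a check of the schedule; the arithmetic shows its size.

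1. **Arm size.** The plan's formula for the Six Minute Walk Test, one-tailed, is N = 2 × ((1.65 + 0.84) × 171.1 / 154.3)². This gives 15.2, rounded up to 16 per group, as stated. With 20% dropout, 16 / (1 − 0.20) = 20 enrolled per group, 40 in total, also as stated. Expected completers are 40 × 0.80 = 32. The point does not rest on this calculation, which only fixes the denominators.

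2. **Present schedule.** Each patient has 12 training sessions and 2 pain readings. The first reading precedes all training. The second follows session 12. No scheduled reading comes between sessions 1 and 12.

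3. **Timing of the last reading.** Of the end visit the Timeline section says "This visit could occur on the same day as the final intervention", but it also allows the visit a day or two later. The documents give no duration for cycling soreness. The statement "This may last for a few days" is in the EMG risk paragraph and concerns irritation and soreness in the tested areas. It cannot be used to show that the ending reading is taken too early.

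4. **Proposed schedule.** A rating at the start of each session adds up to 12 readings, making 14 per patient instead of 2. The rating before session 1 precedes all training, so 12 − 1 = 11 of them follow a session.
   - If all 40 patients complete: 40 × 11 = 440 post-session readings, out of 40 × 12 = 480 added.
   - For 32 completers: 32 × 11 = 352.

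5. **What a by-arm table could show.** If no patient in an arm reports a given harm, the one-sided 95% upper limit for the true rate is 1 − 0.05^(1/n). This is 13.9% for n = 20 and 17.1% for n = 16. For the proportion of patients with soreness, the rates below are assumptions, not figures from the documents (two-sided 0.05):
   - 20% against 40%: power 28% with 20 per arm, 23% with 16.
   - 20% against 60%: power 75% with 20 per arm, 65% with 16.

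   Even a doubling of the rate would usually be missed, so the table can only be descriptive.

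6. **Healthy controls aged 50 to 85.** They complete the measures at the beginning and then train up to 5 times, possibly on eccentric force control. No post-training pain reading is described. They are not randomized, so this bears on tolerability in that group and not on the arm comparison.

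**The case against.** A reader might infer more than the text supports, and the other side is right on several counts.

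- **That soreness is expected to be worse in the robotic arm.** The Cycling paragraph says only that robotic control may increase soreness. The control cycle is also motor-driven: "a motor provides assistance or resistance to compensate for the performance of the patient". An arm difference is a fair inference, since the possible robotic tasks include rewarding forces against pedal motion, but the plan does not predict one. Nor does it call soreness the main risk.
- **That harm during training goes uncaptured.** Problems are reviewed when they arise and sessions are supervised. What is missing is systematic solicitation, especially of soreness felt between visits.
- **That pain cannot be compared by arm.** On its wording, the Group by Time model includes the pre/post pain score, and nothing prevents a tabulation of events by arm. But two readings miss what resolves between them, and the tabulation is not planned.
- **That the schedule excludes other readings.** The assessment list does not say only, and EMG and the questionnaire, also on it, are used at sessions. For those two the text says so; for the Pain Scale it does not.
- **That the daily form contains no pain item.** The form is not in the documents, so this cannot be confirmed. If it has one, the protocol should say so.

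The objection that the gap does not affect the sample size is also correct. This is a matter of safety and tolerability data in a low-risk pilot.

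**Conclusion.** The point holds in a limited form. As described, pain is scheduled at 2 time points around 12 sessions, session-level soreness is not systematically solicited, and no adverse-event summary by arm is planned. Soreness that arises and resolves between the two readings is recorded only if volunteered or observed, and the ending score may be absent for some of the expected 20% who drop out.

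This rests on reading the list's introductory sentence as the full pain schedule and the description of the daily questionnaire as complete. A pain item on the actual form would close most of the gap. The documents do not support a claim of predicted excess soreness in the robotic arm or of harm going wholly unrecorded. The gain is better descriptive tolerability data, with no power to test a difference between arms. It is an inexpensive improvement and leaves the planned gait and fMRI analyses unchanged.

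**What to change.** - Add the existing 0-to-5 Pain Scale, with site (leg muscle, leg joint, skin under the electrodes), to the questionnaire already given at the start of each training session in both stroke arms. Do the same for the trained healthy controls if they use that form. If the form already asks about pain, state this in item 15.
- Have the person running the session read the rating when it is completed and pass any rise to the principal investigator under the Data and Safety Monitoring Plan. That plan allows two weeks for review of behavioral measures, so the quicker route should be written down. Any change to training in response is for the investigators to set.
- Add a sentence to the Behavioral Data section: per-session pain and adverse events will be reported descriptively by arm, including readings from patients who later drop out.
- A brief contact after the last session is optional. It would cover session 12 more fully, but the documents give no duration for cycling soreness from which to time it.

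Cost: under a minute per session on a form already in use, and one extra descriptive table. The main changes need no new visit or procedure.
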